## 6.6 Analysis of Primary Safety Endpoint

The primary safety endpoint is defined as the incidence of neurological death or major ipsilateral stroke (National Institute of Health Stroke Scale [NIHSS] increase of  $\geq 4$  for  $>24$  hours) at any time during the follow-up period (12 months  $\pm$  8 weeks). Total number and frequency of subjects with neurological death or major ipsilateral stroke will be presented with two-sided 95% confidence intervals of the rate.

The primary safety endpoint will be met if the upper bound of the confidence interval is  $\leq 15\%$ . Table 6-3 below summarizes the clinical outcomes of the three studies from the background that specifically address endovascular treatment of wide-necked basilar and MCA aneurysms. Information about these studies is summarized in Section 5, “Background for Proposed Trial”. A complication rate was identified for each article by including events which could indicate stroke (i.e., thromboembolic events, ischemic events, artery dissection, hemorrhage, aneurysm rupture, and cranial nerve palsy). The overall weighted average of the incidence rate derived from the meta-analysis of these three trials was 13%. This provides the basis for selecting 15% for the primary safety endpoint of the Barrel study.

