### 8.1 Primary Outcome Measures

#### 8.1.1 Primary Endpoints

- Primary Efficacy Endpoint: The number of Barrel® VRD treated aneurysms achieving Raymond Grade I (100% occlusion) at 12 months  $\pm$  8 weeks in the absence of retreatment, parent artery stenosis ( $> 50\%$ ), or target aneurysm rupture. The primary efficacy endpoint will be met if the lower bound of the 95% confidence interval is  $> 23\%$ .
- Primary Safety Endpoint: Incidence of neurological death or major ipsilateral stroke (National Institutes of Health Stroke Scale [NIHSS] increase of  $\geq 4$  for  $>24$  hours) at any time during the follow-up period (12 months  $\pm$  8 weeks). The primary safety endpoint will be met if the upper bound of the confidence interval is  $\leq 15\%$ .

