**Table 12-1 Schedule of Tests**

Tests and Evaluations	Screening/ Baseline	Procedural (Day 0)	30 days ±14 days	180 days ±30 days	12 months ±8 weeks	Unscheduled Visit
Inclusion/Exclusion	X					
Demographics	X					
Medical history	X					
Medications	X	X	X	X	X	X
Blood Labs	X					
Modified Rankin Score	X		X	X	X	
NIHSS Score	X			X	X	X 
Adverse Events		X	X	X	X	X
Angiography 	X 	X		X 	X	
Raymond Grade Scale	X 	X		X	X	

MRA is acceptable if performed according to the standard of practice at the participating institution.

The baseline angiogram must be taken no more than 180 calendar days prior to the procedure.

For previously coiled aneurysms

If an angiogram is performed as standard patient care it should be sent to the core laboratory for analysis.

If visit is related to target aneurysm or potentially associated adverse event

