### 12.6.3 Immediate Post-operative Evaluations

The following information will be recorded during the immediate post-operative evaluation:

- Angiographic assessment
  - Stenosis
  - Raymond Grade

Class 1: Complete occlusion - complete obliteration of the aneurysm.

Class 2: Residual neck - persistence of any portion of the original defect of the arterial wall as seen on any single projection, but without opacification of the aneurysmal sac.

Class 3: Residual aneurysm - opacification of the aneurysmal sac.

- Description of adverse events
- Medications

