### 12.6.5 Follow-Up (30-day, 180-day, and 12-month)

The following assessment will be completed at the specified time points below. All visits should be completed by study subjects with successful implant of the Barrel VRD. Subjects that underwent attempted delivery with the Barrel VRD, but were not implanted should complete the 30-day visit and be exited from the study.

- 30 Day  $\pm$  14 Days
  - Neurologic Evaluation
    - The Investigator is responsible for ensuring that the administration of the modified Rankin Score is conducted by a trained person with appropriate qualifications to perform these evaluations.
  - Details of any additional (subsequent) procedures or additional treatments
  - Description of adverse events, including the time of onset
  - Medication Usage
  - 30 day evaluations may be performed remotely via telephone if subject is not available for a visit to the study center.

- 180 Day  $\pm$  30 days
  - Neurologic Evaluation
    - The Investigator is responsible for ensuring that the administration of the NIHSS and modified Rankin Score are conducted by a trained person with appropriate qualifications to perform these evaluations.
  - Details of any additional (subsequent) procedures or additional treatments
  - Angiographic assessment (if done as standard of care)
    - Stenosis
    - Raymond grade
  - Description of adverse events, including the time of onset
  - Medication Usage
- 12 month  $\pm$  60 days
  - Neurologic Evaluation
    - The Investigator is responsible for ensuring that the administration of the NIHSS and modified Rankin Score are conducted by a trained person with appropriate qualifications to perform these evaluations.
  - Details of any additional (subsequent) procedures or additional treatments
  - Angiographic assessment
    - Stenosis
    - Raymond grade
  - Description of adverse events, including the time of onset
  - Medication Usage

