- Subjects presenting with clinical signs and symptoms suggestive of subarachnoid hemorrhage, intracerebral hemorrhage, or cerebral infarction.

The definition excludes:

- Slowly progressive cranial nerve palsies or progressive visual field deficits due to continued aneurysm growth.
- Stroke events in cases of blood disorders such as leukemia or external events such as trauma.
- Transient ischemic attacks, in which the symptoms resolve on their own within 24 hours

Stroke severity will be graded by the CEC as major or minor:

- Major Stroke: A stroke which increases the NIH Stroke Scale of the subject by  $\geq 4$ .
- Minor Stroke: A stroke which increases the NIH Stroke Scale of the subject by  $\leq 3$ .

The term “ipsilateral” in the primary safety endpoint definition will be defined as “on the same side of the brain as the target aneurysm” for MCA aneurysms and as “in the territory supplied by the treated artery” for basilar aneurysms.

Each stroke event will be adjudicated for “Ipsilateral” site of occurrence:

- Ipsilateral for MCA strokes
- In the territory supplied by the treated artery for Basilar artery strokes as adjudicated by the Clinical Events Committee

A **Neurological Death** is any subject death due to neurological reasons.

An **Intra-Cranial Hemorrhage (ICH)** is a hemorrhage within the fixed vault of the cranium (skull). These will be further categorized as:

- **Intra Cerebral Hemorrhage:**
  - Intra Ventricular Hemorrhage (IVH): Hemorrhage within the ventricles
  - Intra Parenchymal Hemorrhage (IPH): Bleeding within the cerebral matter (brain parenchyma), not involving the ventricles

\*Acute Ischemic Stroke with hemorrhagic transformations included in IPH will be explained in comments.
- **Sub Arachnoid Hemorrhage (SAH)**
  - A subarachnoid hemorrhage is bleeding into the subarachnoid space—the area between the arachnoid membrane and the pia mater surrounding the brain
- **Sub-Dural Hematoma (SDH)**
  - Subdural hematoma occurs when there is tearing of the bridging vein between the cerebral cortex and a draining venous sinus
- **Epidural Hematoma (EDH)**
  - A rapidly accumulating hematoma between the dura mater and the cranium

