### **14.8.7 Clinical Events Committee**

A CEC will be in place for the study using a minimum of three (3) physicians knowledgeable in the appropriate disciplines and medical specialties pertinent to the disease state being evaluated in this clinical study. All AEs will be collected and documented prior to adjudication by the CEC. This committee will be responsible for the review and adjudication to the study endpoints of the following events reported by the site:

1. Neurological adverse events with a corresponding worsening of NIHSS
2. All Device related adverse events
3. All Procedure related adverse events
4. All SAEs
5. All Antiplatelet therapy related events

The CEC will independently adjudicate to specified endpoint event definitions, event relatedness, event severity, and event outcomes.

The CEC can request additional source documentation and any potential imaging obtained in support of the adverse event to assist with adjudication.

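### Major stroke in the primary safety endpoint is graded on NIHSS change, but no NIHSS is required during the index hospital stay or at the 30-day visit

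*Protocol*

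**What the plan says.** Protocol sections 6.6 and 8.1.1 define the primary safety endpoint as neurological death or "major ipsilateral stroke (National Institute of Health Stroke Scale [NIHSS] increase of" at least 4 for more than 24 hours, counted "at any time during the follow-up period". Section 12.8.1 has the Clinical Events Committee (CEC) split strokes by the same scale: "Major Stroke: A stroke which increases the NIH Stroke Scale of the subject by" 4 or more, and minor if by 3 or less. On the decision rule, section 6.6 says: "The primary safety endpoint will be met if the upper bound of the confidence interval is" at most 15%.

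The NIHSS row is the same in Tables 3-1 and 12-1. It is marked at baseline, 180 days and 12 months, and at unscheduled visits with the footnote "If visit is related to target aneurysm or potentially associated adverse event". The cells for Day 0 and 30 days are empty.

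The text agrees with the tables. The procedural list (12.6.2) has no NIHSS. Section 12.6.3 opens with "The following information will be recorded during the immediate post-operative evaluation" and then names angiographic findings, adverse events and medications. Section 12.6.5 names only the modified Rankin Score at 30 days, whereas it names both scales at 180 days and 12 months. It adds that "30 day evaluations may be performed remotely via telephone if subject is not available for a visit to the study center".

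**The concern.** Procedural and early post-procedural strokes are a central risk of an implant placed in an intracranial artery, and the endpoint is meant to count them. Whether such a stroke counts depends on two facts: how far NIHSS rose, and whether the rise lasted beyond 24 hours. The protocol requires no measurement that would establish either fact during the index stay or at 30 days.

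A score taken five to seven months later cannot supply them if the subject has partly recovered. The endpoint is judged against a fixed limit in a single-arm study, so there is no control arm in which the same loss would occur. Any under-grading acts in one direction, towards meeting the limit.

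**Working it through.** **1. Timing of the first scheduled score.** The 180-day visit has a window of 30 days either side: 180 − 30 = 150 and 180 + 30 = 210. The first scheduled post-procedure NIHSS falls on day 150 to 210.

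**2. What is required, by period.**

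| Period | NIHSS required? | Source |
|---|---|---|
| Baseline | Yes | Tables 3-1, 12-1; 12.6.1 |
| Procedure and index stay | No | Tables; 12.6.2; 12.6.3 |
| 30 days | No (modified Rankin Score only; telephone allowed) | Tables; 12.6.5 |
| Visit to the investigator for the target aneurysm or an associated event | Yes | 12.6.6; table footnote 5 |
| 180 days and 12 months | Yes | Tables; 12.6.5 |

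Section 12.6.6 speaks of a visit by the subject to the investigator. A stroke in the angiography suite or on the ward before discharge is not plainly such a visit. Nothing in the protocol asks for a second score after 24 hours.

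**3. Subjects without an implant.** Section 6.5 puts everyone with attempted delivery in the ITT set. Sections 12.6.5, 12.6.7 and 12.6.8.2 have those not implanted leave after the 30-day visit. They have no scheduled NIHSS after baseline.

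**4. How close the decision rule is (illustration).** The protocol asks for a two-sided 95% interval for safety but does not name the method. I assume an exact (Clopper-Pearson) interval. The upper limit for x events in n subjects is the 0.975 quantile of a Beta(x + 1, n − x) distribution. I use n = 119 (treated) and n = 107 (evaluable after 10% loss), both from section 6.

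| n | Events | Rate | Exact upper limit | Limit of 15% |
|---|---|---|---|---|
| 119 | 10 | 8.4% | 14.9% | met |
| 119 | 11 | 9.2% | 15.9% | missed |
| 107 | 8 | 7.5% | 14.2% | met |
| 107 | 9 | 8.4% | 15.4% | missed |

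With a Wald interval, p + 1.96 × √(p(1 − p)/n), the limit is met with up to 11 of 119 (14.4%) or 10 of 107 (14.9%), and missed with one more (15.5% and 16.0%).

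**5. What under-counting would do (illustration).** Suppose the true rate is 15% and a share s of endpoint events goes uncounted. The observed rate is then 0.15 × (1 − s), and the chance of meeting the limit is P(X ≤ c), with X binomial and c = 10 (n = 119) or 8 (n = 107). The shares are assumptions; the protocol gives nothing from which to estimate them.

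| s | Observed rate | n = 119 | n = 107 |
|---|---|---|---|
| 0 | 15.0% | 2.4% | 1.5% |
| 10% | 13.5% | 6.1% | 3.9% |
| 20% | 12.0% | 14.1% | 9.3% |
| 30% | 10.5% | 28.4% | 19.7% |

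Neurological deaths need no NIHSS, so s applies to all endpoint events only in so far as they are non-fatal strokes.

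**The case against.** Strokes are adjudicated from event records, not only from scheduled scores. Adverse events are collected from consent to study exit (12.8). A periprocedural stroke with a 4-point deficit lasting over a day would very likely qualify as serious, and serious events are reported within 72 hours with supporting documents (12.8.3). The CEC's first trigger, "Neurological adverse events with a corresponding worsening of NIHSS", presupposes a measured score. Its other triggers do not: it also reviews all serious events and all device- or procedure-related events, and it may request further source documents and imaging (14.8.7). After discharge, section 12.6.6 calls for NIHSS at event-related visits.

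All of this stands, and it rules out three stronger readings that a reader might infer:

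- **That early strokes cannot be graded or would be missed.** They should reach the CEC, and many hospitals may chart a score. What is missing is a required score on which to base the grade.
- **That a downward bias is established.** Nothing tells the CEC to take the day-180 score as the severity of an early stroke. Under-grading is a possibility, not a demonstrated result.
- **That one unclassified stroke decides the endpoint.** This holds only if the count lands on the boundary, as with any threshold, and the boundary moves with the interval method and the denominator.

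The telephone option is also secondary, because the 30-day visit has no NIHSS even when held in person.

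The safeguards do not close the gap. They bring the event to the committee but do not create the measurement on which it must grade.

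**Conclusion.** The point holds in a limited form. No NIHSS is required during the index stay, after 24 hours, or at 30 days, although the non-fatal part of the primary safety endpoint is defined by that scale. Subjects with a failed implantation have no scheduled score after baseline. The grade and the 24-hour persistence of an early stroke would rest on whatever each site happened to record, which may favour the device.

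The schedule facts are certain, because the tables and the text agree. The direction of any error is plausible, but its size is unknown. The event cut-offs assume an exact interval, and the under-counting figures assume both a true rate of 15% and the shares shown. Neurological deaths and the sample size are unaffected. A later analysis plan cannot repair this, since it cannot recover a score that was never taken. The change is advisable and cheap.

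**What to change.** - Add NIHSS after the procedure (at 24 hours or discharge) and at the 30-day visit to Tables 3-1 and 12-1 and to sections 12.6.3 and 12.6.5. The 30-day score also gives subjects without an implant a post-baseline value before they leave.
- Extend section 12.6.6 so that any suspected stroke, including one during a hospital stay, has NIHSS at onset and again after 24 hours.
- Where the 30-day contact is by telephone, require an in-person NIHSS if the modified Rankin Score has worsened.

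This needs a protocol amendment to the assessment schedule, using a short score that sites already administer at baseline, 180 days and 12 months. The cost is a little more site work and possibly a higher observed event rate. The number of subjects does not change.

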### **12.6.6 Unscheduled Visits**

Any visit by the subject to the Investigator related to the target IA treated or a potentially associated adverse event should include a neurologic examination using NIHSS. The Investigator should document the review of the adverse event status and all relevant medications taken by the subject.

### **12.6.7 Study Exit**

Upon completion of the specified study follow-up at 12 months the subject will be exempt from further data collection. The subject will be seen by the treating physician according to standard care following intracranial aneurysm treatment. If the subject underwent attempted delivery with the Barrel VRD but did not receive a Barrel VRD implant, the subject will be exited from the study following the 30 day visit.

### **12.6.8 Termination of Subject Participation**

Subjects may withdraw from the study at any time without penalty or loss of medical care, or they may be withdrawn at any time at the discretion of the Principal Investigator (PI) or Sponsor for safety or administrative reasons.

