### 6.5 Statistical Analysis Sets

The primary analysis set will be based on the intention-to-treat (ITT) population set. For this study, all subjects who meet the study entry criteria, sign the written informed consent (enrolled), and undergo attempted delivery with the Barrel VRD will be counted in the primary analysis set of ITT.

Analysis will also be performed on the per-protocol population set, defined as all subjects included in the ITT population set who have complied with the protocol without major protocol deviations, and have completed the 12-month angiographic evaluation.

The primary analyses for both the safety and effectiveness endpoints will be based on the observed data.

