### **12.6.8.1 Subject withdrawal**

All enrolled subjects have the right to withdraw their consent at any time during this study. All data collected until the time of subject withdrawal will remain in the study database and will be used for analysis. Whenever possible, the site staff should obtain written documentation from the subject who wishes to withdraw his/her consent for future follow-up visits. If the site staff is unable to obtain written documentation, all information regarding the subject's withdrawal must be recorded in the subject's medical record. In addition, the appropriate eCRFs must be completed for the subject and clear documentation of the subject's withdrawal should be provided to the Sponsor.

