### **12.6.8.2 Subject discontinuation by investigator**

An Investigator may discontinue a subject from the study, with or without the subject's consent, for any reason that may, in the Investigator's opinion, negatively affect the well-being of the subject. If a subject is withdrawn from the study, the Investigator will promptly inform the subject and Sponsor. If a subject is enrolled and undergoes attempted delivery with the Barrel VRD without successful implant of the investigational device, the subject will be exited from the study following the 30 day visit.

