### **12.6.8.5 Study Discontinuation by Sponsor**

The Sponsor may choose to discontinue the study should the Sponsor discover additional information during the study that may cause harm to subject safety.

If the study is terminated prematurely or suspended, the Sponsor will promptly inform all clinical Investigators of the termination or suspension and the reason(s) for this. The IRB/EC will also be informed, either by the Sponsor or Investigator if a local IRB/EC is utilized, promptly and provided with the reasons(s) for the termination. If applicable, regulatory authorities will be informed. Enrolled subjects will be asked to complete all remaining study visits and the subject will then be seen by the treating physician according to standard care following intracranial aneurysm treatment.

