## 12.8 Adverse Event Reporting

All adverse events will be collected during the course of the study on the eCRFs.

Adverse event status will be evaluated throughout the study. These will include events occurring from the point of consent until a subject exits the study. Investigators must obtain all information available to determine the causality and outcome of the AE and to assess whether it meets the criteria for classification as a serious and/or unexpected event requiring notification to the Sponsor, regulatory agency, and as applicable, IRB/EC, within the specified reporting timeframe. AEs will be categorized using the definitions in **Section 12.8.1**.

All study AEs, as well as the treatment and follow-up required, should be documented in the subject's medical records and in the eCRF. All study AEs will be followed by the Investigator until resolution or until the end of the 12 month follow-up. A list of potential anticipated adverse events is provided in **Section 13**.

All relevant medical conditions reported at screening/baseline visit will be recorded in the medical history form, including any signs and symptoms related to the condition of intra-cranial aneurysm.

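### The investigator or sponsor may withdraw an implanted subject from the whole study without any endpoint follow-up afterwards, which can bias observed-data results in favour of the device

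*Protocol*

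**What the plan says.** **Who may end participation.** Section 12.6.8 provides that, besides leaving by their own choice, "they may be withdrawn at any time at the discretion of the Principal Investigator (PI) or Sponsor for safety or administrative reasons". Section 12.6.8.2 adds a power on well-being grounds, judged by the investigator and usable without consent if need be: "An Investigator may discontinue a subject from the study". In both places the exit is from the study, not from a test or a treatment.

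**What is kept.** Section 12.6.8.1, written for subjects who withdraw consent, says: "All data collected until the time of subject withdrawal will remain in the study database and will be used for analysis". No section states which assessments continue after a discontinuation by the investigator or sponsor.

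**Adverse events.** Section 12.8 gives the collection window: "These will include events occurring from the point of consent until a subject exits the study". The same section adds: "All study AEs will be followed by the Investigator until resolution or until the end of the 12 month follow-up".

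**When the sponsor stops the whole study.** Section 12.6.8.5: "Enrolled subjects will be asked to complete all remaining study visits".

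**Analysis.** Section 6.5: "The primary analyses for both the safety and effectiveness endpoints will be based on the observed data". Section 6.10 plans multiple imputation under missing at random (MAR) to assess the impact of missing efficacy data. Section 6.2, however, still describes an intention-to-treat method in which subjects lost to follow-up count as failures.

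**The concern.** The study treatment is a single implantation. Once the device is detached, removing a subject from the study takes away no device exposure; it only stops the trial from seeing what happens next. Safety and well-being are named grounds for removal, and a subject about whom the investigator is worried on those grounds may plausibly have a worse prognosis than the rest.

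For such a subject exit means three losses:

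- any first neurological death or major ipsilateral stroke after exit;
- the 12-month Raymond grade and stenosis reading, on which efficacy success depends;
- the 12-month NIHSS and mRS.

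If the missing subjects do worse than those observed, an observed-data analysis overstates the occlusion rate and understates the event rate. Imputation under MAR corrects this only as far as the recorded covariates explain the difference. The imputation in section 6.10 is also aimed at efficacy, so it gives the safety endpoint no protection.

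**Working it through.** **Inputs from the protocol.** Null rate 28%, one-sided alpha 0.025, exact binomial test and exact 95% interval (6.2, 6.3); expected rate 41%, 10% dropout, 119 treated (6.3); 107 evaluable (6); safety met if the upper 95% limit is at most 15% (6.6).

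**Assumptions.** The number and outcomes of discretionary withdrawals are mine; the protocol gives neither. I use exact (Clopper-Pearson) limits for safety as well, although 6.6 does not name the interval. I take the 28% goal of 6.3; section 8.1.1 still states 23%, and against 23% every efficacy example below would pass.

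**Step 1: the plan's own figure.** With n = 107, the smallest r with P(X ≥ r | 0.28) ≤ 0.025 is r = 40 (attained alpha 0.0221). Power is P(X ≥ 40 | 0.41) = 0.804, and 107 / 0.90 = 118.9, so 119 treated. Both figures reproduce.

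**Step 2: efficacy at the boundary.** Lower limit = Beta quantile(0.025; x, n − x + 1), where x is the number of successes.

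| Result | Meaning | Lower limit | Against 28% |
|---|---|---|---|
| 40/107 | observed cases, smallest passing count | 28.2% | met |
| 40/108 | one withdrawn failure added back | 27.9% | not met |
| 40/110 | three added back | 27.4% | not met |
| 41/110 | one more success, three added back | 28.2% | met |

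The flip therefore needs a result exactly at the boundary. One extra success absorbs three hidden failures.

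**Step 3: false-success probability.** Let the true success rate among all 119 be 28%, and suppose k withdrawn subjects are all failures. The rate among those observed is then 0.28 × 119 / (119 − k). Applying the exact rule at n = 119 − k:

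| k | n | observed rate | required successes | P(efficacy success) |
|---|---|---|---|---|
| 0 | 119 | 28.0% | 44 | 0.021 |
| 3 | 116 | 28.7% | 43 | 0.032 |
| 6 | 113 | 29.5% | 42 | 0.048 |
| 9 | 110 | 30.3% | 41 | 0.070 |
| 12 | 107 | 31.1% | 40 | 0.100 |

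The last row puts the whole planned dropout into this category and makes every one a failure. It is an outer bound, not a forecast.

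**Step 4: safety.** Upper limit = Beta quantile(0.975; x + 1, n − x), where x is the number of events. Suppose one event occurs after exit and is not recorded.

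| Handling of the withdrawn subject | As analysed | With the event recorded |
|---|---|---|
| kept as event-free | 10/119: 14.9%, met | 11/119: 15.9%, not met |
| dropped from the denominator | 10/118: 15.03%, not met | 11/119: 15.9%, not met |
| dropped, one event fewer | 9/118: 14.0%, met | 10/119: 14.9%, met |

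In these cases a single missed event changes the safety verdict only if the withdrawn subject stays in the denominator as event-free.

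**The case against.** The strongest opposing case is that this is a general permission with limited reach, and much of it stands.

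- **It is permissive.** A reader might infer that missingness is tied by rule to poor outcome. The text does not support that: no section says that a stroke, retreatment or poor grade leads to exit, and administrative reasons are listed beside safety with no shown link to outcome.
- **Events before exit are not lost.** The safety endpoint counts an event at any time, so a subject withdrawn after a major ipsilateral stroke is already an event. Retreatment and rupture before exit already make the aneurysm an efficacy failure. Section 12.6.8.1 keeps data gathered before withdrawal (for consent withdrawal, but there is no reason to read it otherwise here), and 12.8 has reported adverse events followed to resolution or 12 months.
- **12.6.8.5 is not a contradiction.** A reader might take it as one. It covers termination of the whole study, whereas 12.6.8 and 12.6.8.2 cover one subject; both can be followed. It does show that the sponsor already regards continued visits as feasible.
- **Missing efficacy data are not ignored.** Section 6.10 plans imputation, and the sample size allows 10% dropout.
- **The safety flip is conditional.** A reader might infer that one unrecorded death overturns the safety conclusion. As shown above, that needs a denominator convention the protocol does not state.

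What survives is narrower: first events after exit, and 12-month assessments, in subjects removed for safety or well-being. None of these points supplies that follow-up. Dropout allowance preserves precision but does not remove bias, and MAR is least secure where the reason for leaving is concern about the subject's condition.

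**Conclusion.** The point holds in this limited form. Sections 12.6.8 and 12.6.8.2 permit an implanted subject to be taken out of all follow-up at the discretion of the investigator or sponsor, and nothing requires endpoint collection afterwards. With observed-data primary analyses, withdrawals for safety or well-being can bias both primary endpoints in favour of the device. Whether they would, and by how much, cannot be read from the documents.

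The size depends on assumed numbers. At the efficacy boundary one hidden failure is enough to reverse the result; one success above it, three are not. If all withdrawn subjects were failures, the false-success probability would rise from 0.021 with none to 0.032 with three and 0.100 with twelve.

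The direction for efficacy also rests on section 6.5 governing. If the rule in 6.2 applied to withdrawn subjects, they would count as failures and the bias would not favour the device. The two sections give different answers and must be reconciled. Section 6.2 concerns occlusion rates, so it does not help the safety endpoint either way.

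This is worth correcting before data accrue, because it is cheap and affects both primary endpoints. It is not evidence that the trial's results would be wrong.

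**What to change.** 1. In 12.6.8 and 12.6.8.2, separate withdrawal of consent from every other discontinuation. State that, once the Barrel VRD is implanted, a discontinuation by the investigator or sponsor does not end follow-up. A subject may be excused from a particular study test, but adverse events, vital status, NIHSS, mRS and available imaging are still collected to the 12-month visit, as 12.6.8.5 already asks when the study is terminated.
2. In 12.8, make the adverse event window for implanted subjects run to 12 months unless consent is withdrawn, the subject dies or is lost to follow-up.
3. Reconcile 6.2 with 6.5, and state how withdrawn subjects count in the numerator and denominator of each primary endpoint.
4. Record the reason for each discontinuation, so that administrative exits can be told apart from those for safety or well-being.

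The right to withdraw consent in 12.6.8.1 is untouched, and no rule on clinical care changes. The sample size stays at 107 evaluable and 119 treated, and the visits are already scheduled in Table 12-1. The cost is protocol wording and a few more contacts with subjects whom sites would otherwise have exited.
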